#### **3.4.2 Secondary Endpoints**

- Safety of the combination of vesigenurtacel-L and BCG (Phase 2 only)
- Safety of high dose vesigenurtacel-L monotherapy (Phase 2 only)
- Proportion of patients with recurrence at 3, 6, 12, 18, and 24 months
- Proportion of patients with progressive disease at 3, 6, 12, 18 and 24 months
- Disease-free survival (DFS) at 3, 6, 18, and 24 months
- Overall DFS
- Overall Survival (OS)
- Proportion of patients undergoing post-treatment TURBT or fulguration by 12 and 24 months
- Proportion of patients undergoing cystectomy by 12 and 24 months
- Proportion of patients with immunologic response of PBMCs via intracellular cytokine staining (ICS) by flow cytometry and/or ELISPOT on CD8+ cells after receiving vesigenurtacel-L treatment as compared to baseline

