### 6.3 Long-term Follow-up Visits

All patients will be followed for the procedures listed below every 3 months from the date of the previous visit for 2 years then every 6 months from the date of the previous visit for a year or until study termination, whichever occurs first:

- Survival
- New anticancer treatments initiated after disease recurrence
- TURBT or fulguration procedures
- Cystectomy

In addition patients who have completed all study treatments or have discontinued study product dosing due to reason other than disease recurrence/progression will have the following procedures performed at each long-term follow-up visit:

- Cystoscopy/Cytology; biopsy if area suspicious for disease recurrence is identified at discretion of investigator (*Note: patients who have a biopsy performed will provide at least 4, non-stained, 10 micron sections for TCR sequencing and analysis of infiltrating T-cells.*) *If slides are not available, FFPE tissue (≥50 microns) is also acceptable.*

If a patient has recurrent/progressive disease and discontinues study treatment, the above disease assessment procedures will be discontinued, and subsequent long-term follow-up visits may be conducted via phone visit.

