## **9.0 CONCOMITANT MEDICATIONS AND NON-DRUG THERAPIES**

### **9.1 Permitted Medications and Non-Drug Therapies**

A single dose of mitomycin C or other standard intravesical treatment administered immediately post-TURBT (for the current occurrence of non-muscle invasive bladder cancer) is permitted according to the investigative center's standard practice.

Maintenance BCG per the institution's standard of care may be administered to patients in Phase 1 at any time. Additional courses of maintenance BCG may be administered to patients in Phase 2 after the completion of study treatment per the protocol.

All concomitant medications, including prescription and over-the-counter medications, taken during the 14 days before the date of first dose, during the study treatment, and through 4 weeks post the last dose of study product will be documented. Any concomitant medication(s), including herbal or vitamin preparations, taken during the study will be recorded in the ECRF. At a minimum, the drug name, dose, and the dates of administration will be recorded. Caffeine consumption will also be collected.

Local and/or systemic injection reactions may be treated with anti-allergics, antipyretics, and/or analgesics in accordance with standard local practice and investigator's clinical judgment.

Pre-treatment of the vaccine injection site with anesthetic cream is allowed only after the Week 1 vaccine administration has been performed without it and injection pain has been documented as an AE.

Repeat TURBT or fulguration procedures will be permitted only in the setting of persistent, recurrent, or progressive disease according to an investigator's standard practice.

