#### **12.5.2.6 Burden of Repeat TURBT**

Defined as the proportion of patients with no repeat TURBT vs 1 TURBT vs 2 TURBT vs 3 TURBT etc within 12 months since randomization, within 18 months since randomization, and within 24 months since randomization.

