2.1 Study Objectives

Primary Objective

- **Phase 1:** To characterize the safety and tolerability of monotherapy vaccination with HS-410 in patients with non-muscle invasive bladder cancer.
- **Phase 2:**
 - Arms 1, 2, and 3: To evaluate 1-year disease-free survival in patients with non-muscle invasive bladder cancer treated with BCG in combination with blinded study product (one of two doses of vesigenurtacel-L or placebo).
 - Arm 4: To evaluate 1-year disease-free survival in patients with non-muscle invasive bladder cancer treated with high dose vesigenurtacel-L monotherapy.

Secondary Objectives

Both Phases:

- To evaluate the proportion of patients with recurrence at 3, 6, 12, 18, and 24 months
- To evaluate the proportion of patients with progressive disease at 3, 6, 12, 18, and 24 months
- To evaluate overall disease-free survival
- To evaluate overall survival (OS)
- To evaluate the proportion of patients undergoing post-treatment TURBT or fulguration by 12 and 24 months
- To evaluate the proportion of patients undergoing cystectomy by 12 and 24 months
- To evaluate the proportion of patients with immunologic response of PBMCs via intracellular cytokine staining (ICS) by flow cytometry and/or ELISPOT on CD8+ cells following vesigenurtacel-L vaccination

Phase 2 only:

- To evaluate the safety of the combination of vesigenurtacel-L and BCG
- To evaluate the safety of high dose vesigenurtacel-L monotherapy

Primary Endpoint

- **Phase 1:** Safety and tolerability of monotherapy vaccination with HS-410 in patients with non-muscle invasive bladder cancer.
- **Phase 2:** 1-year disease-free survival in patients with non-muscle invasive bladder cancer treated with BCG in combination with one of two doses of HS-410 or placebo, or with high dose HS-410 without BCG. The 1-year disease-free survival rate is defined as the proportion of patients who are alive and free from recurrence and progression at 12 months following randomization.

Secondary efficacy endpoints:

Both Phases:

- Proportion of patients with recurrence at 3, 6, 12, 18, and 24 months from randomization, estimated based on Kaplan-Meier curves. Recurrence is defined as disease that has recurred to the same extent of disease (ie same stage / severity) or to a lower stage/severity of disease compared to screening.

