- Proportion of patients with progressive disease at 3, 6, 12, 18, and 24 months from randomization. Progressive disease is defined as an increase in T stage from TIS or Ta (at screening) to T1 (lamina propria invasion), development of T2 or greater or lymph node (N+) disease or distant metastasis (M1), or an increase in grade from low to high per the IBCG recommendations.
- Disease-Free survival at 3, 6, 18, and 24 months from randomization. A patient is considered as disease-free at a timepoint if the disease has not recurred nor progressed, and the patient is still alive.
- Overall Disease free survival (DFS): DFS is the time from randomization until the day of disease recurrence or progression
- Overall survival (OS): OS is the time from randomization until the day of death by any cause or censoring
- Proportion of patients undergoing a repeat TURBT by 12 months and by 24 months from randomization
- Proportion of patients undergoing cystectomy by 12 months and by 24 months from randomization
- Immunological response (IR): Peripheral blood immunological response via intracellular cytokine staining (ICS) by ELISPOT of on CD8+ cells following HS-410 vaccination will also be evaluated

Phase 2 only:

- Safety of the combination of vesigenurtacel-L and BCG
- Safety of high dose vesigenurtacel-L monotherapy

Exploratory Endpoints

In patients completing at least 6 weekly doses of study medication, the following exploratory endpoints will be evaluated:

- Immunologic response of PBMCs (analysis of surface markers, CD3, CD4, CD8, degranulation) and stimulation analysis via ICS of IFN- γ , IL-2, TNF α and perforin.
- Total PBMC counts by flow cytometry, including lymphocyte subsets (B cells, helper T-cells, cytotoxic T-cells, NK cells and T-reg)

- Evaluation of tumour tissue obtained from pre-treatment resection for antigen expression by immunohistochemical analysis
- Evaluation of tumour tissue obtained from repeat biopsy, if clinically indicated, for presence of infiltrating T-lymphocytes
- T cell receptor sequencing of peripheral blood T cells before and during the course of treatment
- Immune cell infiltration and inflammatory cytokine levels in urine (phase 2 only)

Safety Endpoints

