- Burden of repeat TURBT, defined as the proportion of patients with no repeat TURBT vs 1 TURBT vs 2 TURBT vs 3 TURBT etc within 12 months since randomization (ie day 366 or earlier), within 18 months since randomization (ie day 548 or earlier) and within 24 months since randomization (ie day 731 or earlier).

For time to recurrence, time to progression, disease-free survival and overall survival, the Kaplan-Meier estimates on the proportion of patients free from the event of interest at 3, 6, 9, 12, 18 and 24 months from randomization will be presented.

For time to cystectomy, the Kaplan-Meier estimates on the proportion of patients with cystectomy at 12, 18 and 24 months from randomization will be presented. In addition, the time to cystectomy from original TURBT will be analysed in a similar way, and the data will be presented as sensitivity analysis.

For intensity of repeat TURBT, the same analysis will be repeated using the 12, 18 and 24 months since original TURBT, as sensitivity analysis.

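### The named endpoint is TURBT or fulguration, but the SAP endpoint and both burden definitions count TURBT only, and the burden measure has no consistent method or rule for cystectomy and death.

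*SAP*

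**What the plan says.** The endpoint list in Protocol 3.4.2 reads "Proportion of patients undergoing post-treatment TURBT or fulguration by 12 and 24 months"; the synopsis and Protocol 2.2 agree. The SAP repeats this as an objective in section 2.1: "To evaluate the proportion of patients undergoing post-treatment TURBT or fulguration by 12 and 24 months".

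Later in the same SAP section, the matching endpoint becomes "Proportion of patients undergoing a repeat TURBT by 12 months and by 24 months from randomization". SAP 7.2 defines the analysis as "Burden of repeat TURBT, defined as the proportion of patients with no repeat TURBT vs 1 TURBT vs 2 TURBT" and so on, within 12, 18 and 24 months of randomization. Protocol 12.5.2.6 carries the same definition: "Defined as the proportion of patients with no repeat TURBT vs 1 TURBT vs 2 TURBT vs 3 TURBT etc within 12 months since randomization", and likewise at 18 and 24 months. None of these three mentions fulguration.

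Elsewhere the protocol names the two procedures side by side. Section 6.3 lists "TURBT or fulguration procedures" among the items collected in long-term follow-up. Section 9.1 states: "Repeat TURBT or fulguration procedures will be permitted only in the setting of persistent, recurrent, or progressive disease". Inclusion criterion 2 accepts either as removal of papillary disease.

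On method, SAP 7.2 puts the burden measure in its list of Kaplan-Meier analyses. Protocol 12.1 names it among the time-to-event endpoints, and Protocol 12.5.2 assigns Kaplan-Meier methods to the secondary efficacy parameters in general. In SAP 7.2 the recurrence, progression, DFS, OS and cystectomy entries each have a censoring rule; the burden entry has none. SAP 5.1 makes the whole analysis set the default denominator for percentages and rules out imputation.

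**The concern.** The quantity to be reported is not the quantity named as the endpoint. Under Protocol 9.1, a fulguration on study means that disease is present. A TURBT-only count nevertheless puts that patient in the zero category with patients who needed no procedure. The omission works in one direction: it can lower the TURBT-or-fulguration rate or leave it unchanged, but never raise it. Section 9.1 also leaves these procedures to the investigator's standard practice, across up to 20 centers, so the share of fulgurations may vary by site.

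The second problem is that a table of patients by number of procedures is not a time-to-event variable, yet it is listed as one. Until the documents choose, two programmers could treat a patient who goes straight to cystectomy, or who dies, in different ways and both claim to have followed the plan.

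**Working it through.** The documents give no planning figure for this endpoint, so there is none to reproduce. The only design figure, 80% power for one-year DFS, is not used here.

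**Step 1. Follow three hypothetical patients through the definitions.**

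| Patient, first 12 months | Protocol 3.4.2 and SAP 2.1 objective | SAP 2.1 endpoint | SAP 7.2 and Protocol 12.5.2.6 |
|---|---|---|---|
| A: recurrence fulgurated, no TURBT | counted | not counted | zero category |
| B: one TURBT, then cystectomy | counted | counted | one TURBT |
| C: cystectomy or death, neither procedure | not counted | not counted | zero category if read as a proportion over the analysis set; presumably censored if read as Kaplan-Meier |

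Patient A is the contradiction. Patient C is the undefined case. Patient B shows that cystectomy or death after a TURBT does not move a patient into the zero category.

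**Step 2. Size of the fulguration omission.** Input: 25 patients per arm (Protocol 3.3). Let T be patients with at least one TURBT and f patients with fulguration only.

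- Reported rate = T/25
- Rate for the named endpoint = (T + f)/25
- Difference = f/25, which is 4 points per patient

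The documents give neither T nor f. With T = 8 assumed and f varied:

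| f (assumed) | TURBT only | TURBT or fulguration | Zero category, TURBT only | Zero category, either procedure |
|---|---|---|---|---|
| 0 | 8/25 = 32% | 8/25 = 32% | 68% | 68% |
| 1 | 32% | 9/25 = 36% | 68% | 64% |
| 3 | 32% | 11/25 = 44% | 68% | 56% |
| 5 | 32% | 13/25 = 52% | 68% | 48% |

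**Step 3. Effect of the undefined handling.** Let c be patients with cystectomy or death and neither procedure. They are in neither T nor f, so no procedure rate in Step 2 changes. Only the content of the zero category does. With T = 8, f = 0 and c = 3 (all assumed), the zero category is:

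- over the analysis set, with the three left in it: (25 − 8)/25 = 17/25 = 68%
- censored before any TURBT occurs (the limiting case): (25 − 8 − 3)/(25 − 3) = 14/22 = 64%
- shown in their own category: (25 − 8 − 3)/25 = 14/25 = 56%

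The same patients give three figures, and the documents do not say which of the first two is meant.

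**The case against.** The best defense is that the protocol still covers the named endpoint. Section 12.1 presents binary secondary endpoints as odds ratios with 95% confidence intervals, and the listed binary endpoint includes fulguration. The exploratory comparison of immune responders with non-responders in 12.5.2.9 also keeps it. This has some force: the general rule arguably reaches the endpoint. But 12.1 refers to the SAP for the exact methods, and the SAP's endpoint and its only specific analysis drop fulguration. The contradiction remains, inside the SAP as well as between documents.

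Three stronger readings are tempting, and the documents do not support them.

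- *The plan puts patients who have a cystectomy or die in the best category.* No section says so. It follows only from the default denominator in SAP 5.1, only for patients with no earlier TURBT, and it conflicts with the Kaplan-Meier heading. Nor do the definitions rank the categories; they count a procedure.
- *Surgical burden as a whole is understated.* Cystectomy is a separate endpoint with its own Kaplan-Meier estimates, deaths enter OS, and a fulgurated recurrence still counts in time to recurrence and DFS. None of these outcomes is hidden.
- *The comparison between arms is biased.* Physician and patient are blinded in Arms 1 to 3, and nothing in the documents suggests that fulguration use differs by arm. Any imbalance has no known direction.

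On weight, SAP 5.5 calls the trial exploratory and restricts p-values to the primary analysis. No decision rule depends on this endpoint. That limits its importance but does not remove the inconsistency.

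**Conclusion.** The point holds in two parts. First, the SAP endpoint and both burden definitions omit fulguration from an endpoint that names it. The reported rate is 4 points too low for each fulguration-only patient in an arm of 25. This rests on the planned arm size and on at least one such patient occurring; the total and any difference between arms cannot be derived from the documents. Second, the burden measure is defined as a proportion, is listed under Kaplan-Meier methods, and has no event or censoring rule. Cystectomy or death without an earlier procedure is therefore undefined. Read as a proportion, it falls in the zero category. It changes what that category contains, not the procedure rate.

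The primary analysis is unaffected. The correction should still be made, because a prespecified secondary endpoint would otherwise be reported in a narrower form than stated.

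**What to change.** 1. In the SAP 2.1 endpoint, SAP 7.2 and Protocol 12.5.2.6, count TURBT or fulguration after randomization (treatment assignment in Arm 4). Carry the same wording into the sensitivity analysis timed from the original TURBT.
2. Report the measure as proportions with 0, 1, 2, and 3 or more procedures. Remove it from the Kaplan-Meier list in SAP 7.2 and from the time-to-event list in Protocol 12.1, and exempt it from the general statement in Protocol 12.5.2.
3. Show cystectomy without a prior procedure, and death without a prior procedure, as separate categories outside 0 procedures. Patients with an earlier procedure stay in their count category. State also how a patient followed for less than the full window is shown, since a proportion has no censoring.

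The cost is a definition and table edit in both documents. Protocol 6.3 already collects both procedures, cystectomy and survival in long-term follow-up. Phase 2 treatment runs to Week 52 with an end-of-treatment visit at Week 56, so most of the 12-month window precedes that follow-up for patients who complete treatment. SAP 2.1 lists concomitant procedures among its assessments; the sponsor should confirm that these include fulgurations during treatment. The downside is that the reported procedure rate will be equal or somewhat higher.

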3.3 Inclusion-Exclusion Criteria and General Study Population

Patients with non-muscle invasive bladder cancer who have undergone TURBT and are judged to be at an increased risk for recurrence are eligible if they are BCG naive or have completed previous BCG treatment >12 months prior to the most recent TURBT are eligible for both the phase 1 or 2 parts of the study. Patients must meet all of the following inclusion criteria to be enrolled into the study:

Inclusion Criteria

1. Willing and able to sign informed consent and comply with the protocol, including clinic visits to receive weekly vesigenurtacel-L injections for 12 doses followed by either monthly vesigenurtacel-L injections for three months in Phase 1 or three courses of three once-weekly injections in Phase 2.
2. Histologically or cytologically confirmed non-muscle invasive bladder cancer [Ta, T1 or Tis (CIS)]. Papillary disease must have been removed by transurethral resection or fulguration.
3. Either
 - i. High-risk disease, defined as T1 and/or high-grade and/or CIS, *or*
 - ii. Intermediate-risk disease defined as Ta low-grade with at least three of the following four risk factors: multiple tumors, tumor size > 3cm, early recurrence (<1 year from previous staging procedure), or recurrence with a frequency of more than once in any 12 month period.
4. Patients must be BCG naive or have completed previous BCG treatment >12 months prior to the baseline staging procedure.
5. For Phase 2 only: Arms 1, 2, and 3: Suitable, in the opinion of the investigator, to receive a 6-week course of induction intravesical BCG in the adjuvant setting within 6 weeks following the baseline staging procedure for the current occurrence of non-muscle invasive bladder cancer. Arm 4: Suitable for monotherapy vaccine administration post-TURBT. For Phase 1 only: Has previously received 3-6 weekly doses of BCG.
6. Age ≥18 years
7. Lab parameters:
 - Albumin ≥2.5 mg/dL
 - Total bilirubin <1.5 mg/dL
 - Alanine transaminase (ALT) and aspartate transaminase (AST) ≤2.5 × upper limit of normal (ULN)
 - Serum creatinine ≤2.2 mg/dL or calculated creatinine clearance >35 mL/minute per the Cockcroft-Gault formula
 - White blood cell (WBC) count ≥4,000/mm³ with an absolute neutrophil count ≥1,500/mm³
 - Hemoglobin ≥9 g/dL
 - Platelet count ≥75,000/mm³

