5.3 Covariates and Subgroups

There will be no covariate or subgroup analysis in the phase 1 component of this protocol.

For the phase 2 component of the study, the following subgroups may be used to further summarize and evaluate the efficacy endpoints, if sufficient data are available:

- Risk of recurrence (High risk vs intermediate risk)
- Carcinoma in situ (yes vs no)
- Patient immune response
- TNM stage, grade, and severity
- BCG naïve or BCG recurrent; number of prior BCG treatments
- Screening TURBT characteristics (Re-resection TURBT at screening, muscle in specimen)
- Number of prior TURBTs
- Number and size of tumors
- TIL status
- Demographics
- Academic vs. Community practices
- Use of Blue Light cystoscopy
- Use of peri-operative chemotherapy

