7.2 Secondary Efficacy Analyses

For time-to-event endpoints (e.g. DFS, OS), Kaplan-Meier / product limit method will be used to estimate the survival distributions over time, and to estimate median time to event. Where appropriate, inference for time-to-event endpoints will be assessed using the Log-rank test statistic, and the treatment effect will be estimated using Cox proportional hazards model. The assumption of proportional hazards will be assessed graphically.

The following will be analysed using Kaplan-Meier time-to-event methodology:

- Time To Recurrence, defined as the time from randomization to recurrence.
 - Recurrence is defined as disease that has recurred to the same extent of disease (ie same stage / severity) or to a lower stage/severity of disease compared to screening.
 - If recurrence has not occurred in a patient, the date of last disease assessment will be used as the timepoint for censoring.
 - The analysis will be repeated in an exploratory manner where recurrence is defined as only those recurrences to the same extent of disease (or greater) as screening.

- Time To Progression, defined as the time from randomization to progression.
 - Progression is defined as an increase in T stage from CIS or Ta (at screening) to T1 (lamina propria invasion), development of T2 or greater or lymph node (N+) disease or distant metastasis (M1), or an increase in grade from low to high per the IBCG recommendations..
 - If progression has not occurred in a patient, the date of last disease assessment will be used as the timepoint for censoring.

- Disease-Free Survival, defined as the time from randomization to recurrence or progression.
 - If a patient has recurred or progressed, then the first date the recurrence or progression has occurred will be used as the timepoint for the event.
 - If a patient has neither recurred nor progressed, then the date of last disease assessment will be used as the timepoint for censoring.

- Overall Survival, defined as the the time from randomization to death.
 - If a patient is still alive, then the patient will be censored on the date of most recent date known alive.
 - If a patient is lost to follow up, then the patient will be censored on the date last known alive.

- Time to cystectomy, defined as the time from randomization to cystectomy.
 - If a patient has not undergone cystectomy, the patient will be censored on the date of last disease assessment.

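### SAP 7.2 restarts the cystectomy clock at an undefined 'original TURBT' with no delayed entry, so that sensitivity analysis gives rates biased low; the matching repeat-TURBT analysis does not say which procedures count.

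*SAP*

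**What the plan says.** The main analysis in SAP 7.2 starts at randomization: "Time to cystectomy, defined as the time from randomization to cystectomy". The list it belongs to opens with "The following will be analysed using Kaplan-Meier time-to-event methodology", and for the time points the SAP says that "the proportion of patients with cystectomy at 12, 18 and 24 months from randomization will be presented". It then moves the origin: "the time to cystectomy from original TURBT will be analysed in a similar way", and "the data will be presented as sensitivity analysis". For repeat TURBT, "the same analysis will be repeated using the 12, 18 and 24 months since original TURBT", again as a sensitivity analysis.

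SAP 7.2 mentions no delayed entry, left truncation or landmark. Nor does it say whether procedures before randomization are counted.

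The original TURBT is defined nowhere. Other sections speak of the most recent TURBT (SAP 3.2), the baseline staging procedure (SAP 3.3) and the screening TURBT (SAP 5.3). Patients may have had earlier disease: "Patients must be BCG naive or have completed previous BCG treatment >12 months prior to the baseline staging procedure". The number of prior TURBTs is a planned subgroup variable, and so is "Screening TURBT characteristics (Re-resection TURBT at screening, muscle in specimen").

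**The concern.** Entry requires a bladder that can still be treated and inspected: papillary disease resected or fulgurated, or CIS; intravesical BCG in Arms 1-3; cystoscopic follow-up for all. A patient who had a cystectomy between the original TURBT and randomization would not be in the trial. That interval is event-free by selection. Ordinary Kaplan-Meier from the TURBT nevertheless puts every patient in the risk set from day 0, which enlarges the denominators and lowers the estimated rate.

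For repeat TURBT the mechanism is different, because patients can and do have TURBTs before entry. If those inside the window are counted, pre-trial procedures enter the outcome. If they are not, each window holds less than its nominal length of post-randomization follow-up.

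At stake is the use of these results as a check on the main analysis. A rate that is low by construction cannot confirm or question the randomization-based rate, and the choice of start date would be left to programming.

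**Working it through.** The documents give no cystectomy rate, so there is no planned figure to reproduce. The rates, the earlier-BCG shares and the long gaps below are assumptions.

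**Inputs from the documents.** Time points of 12, 18 and 24 months (SAP 7.2). First dose within 6 weeks (42 days) of the most recent procedure in Phase 2 (SAP 3.2), and 8-12 weeks (56-84 days) after it in Phase 1 (Protocol 6.1.1, footnote 3). At most 3 days between randomization and first dose (SAP 3.5). Earlier BCG finished more than 12 months before baseline staging (SAP 3.3, criterion 4).

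**Formula.** With constant hazard h, the true risk by time t after TURBT is 1 − exp(−h·t). If a patient enters event-free after a gap L, ordinary Kaplan-Meier from TURBT targets 1 − exp(−h·max(0, t − L)).

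**Reading A: original = baseline procedure.** Assume a 12-month rate of 10%: h = −ln(0.90)/12 = 0.00878 per month. The true rates are 10.0%, 14.6% and 19.0%.

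| Gap | 12 mo | 18 mo | 24 mo |
|---|---|---|---|
| 4 weeks (0.92 mo), also the average over 2-6 weeks | 9.3% | 13.9% | 18.3% |
| 6 weeks (1.38 mo) for everyone | 8.9% | 13.6% | 18.0% |

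For the second row at 12 months: 1 − exp(−0.00878 × 10.62) = 8.9%.

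A simulation of 20,000 patients with gaps of 2-6 weeks gave 9.7%, 14.3% and 18.7%, against 10.1%, 14.7% and 19.1% with delayed entry. That sample ran slightly high (10.4% at 12 months from randomization), so 9.3% is the expected value. With the 6-week gap for everyone, an assumed 5% becomes 4.4% and an assumed 20% becomes 17.9% at 12 months.

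The observable part of a 365-day window is (365 − 42)/365 = 88.5% at the Phase 2 limit. In Phase 1 it is (365 − 56)/365 = 84.7% down to (365 − 84)/365 = 77.0%, for 10 patients.

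**Reading B: original = first-ever TURBT.** At L = 12 months the 12-month rate is 0% by construction; with the 10% assumption, the 18- and 24-month rates are 5.1% and 10.0% instead of 14.6% and 19.0%. At L = 24 months all three are 0%.

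Such gaps are plausible. A first TURBT that preceded earlier BCG lies more than 12 months back. Every intermediate-risk patient also has earlier disease, because three of the four risk factors cannot be met without one of the two recurrence factors.

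For a mixture, assume a 24-month risk of 10% from randomization (12-month risk 5.1%). Let a share p have gaps of 13-60 months and the rest 0.3-1.4 months. At 12 months the long-gap patients contribute nothing, so the estimate is about (1 − p) × 0.93 of the truth, where 0.93 is the p = 0 result:

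| p | 12 mo, formula | 12 mo, two simulations | 24 mo, two simulations |
|---|---|---|---|
| 20% | 0.74 | 0.72, 0.74 | 0.78, 0.79 |
| 35% | 0.60 | 0.59, 0.61 | 0.65, 0.67 |
| 50% | 0.47 | 0.45, 0.46 | 0.50, 0.49 |

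Under a different assumption (10% at 12 months, half the patients dated 3-36 months back), ordinary Kaplan-Meier gave 5.6%, 8.9% and 12.7%; delayed entry gave 9.6%, 14.1% and 18.7%.

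**Repeat TURBT.** No rate calculation applies. Protocol 6.2.2 has the dates of all procedures for the current occurrence captured, so a re-resection after the original TURBT is on file and inside the window. The stated objective concerns post-treatment TURBT or fulguration (Protocol 2.2, SAP 2.1). SAP 7.2 does not say which of the two governs the shifted window.

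**The case against.** The strongest reply is that the term most naturally means the initial resection of the current occurrence, as opposed to a re-resection. Dates are captured for that occurrence, and no collection of first-ever TURBT dates is described. On that reading the loss is about one percentage point or less at a 10% rate. Even on the other reading, 25 patients per arm at 5.1% yield about 1.3 cystectomies by 12 months, and a fall to 2.3% is 0.7 of a patient. Both analyses are labelled sensitivity analyses and stand beside randomization-based ones. All of this stands and limits the importance. It does not remove the bias: under either reading the stated method puts patients at risk before they could have an event.

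A reader might infer three stronger things that the documents do not support.

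- **That pre-trial TURBTs will be scored as outcomes.** The SAP does not say so, and the post-treatment wording of the objective points the other way. It is an open question.
- **That these results would say nothing about the vaccine, or would favour an arm.** Arms 1-3 are randomized with stratification by risk and CIS, so the gap is balanced in expectation. Chance imbalance is possible: with an assumed 35% share, two arms of 25 differ by 5 or more earlier-BCG patients about 18% of the time. That is a hazard of any unadjusted comparison of this size. Arm 4 is not randomized, but comparisons with it are declared exploratory.
- **That patients with fulguration only or CIS only would be dropped.** They may lack a TURBT date, but no exclusion is stated, and the SAP at times uses TURBT loosely for the entry procedure.

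**Conclusion.** The point holds for the cystectomy sensitivity analysis. Time before randomization or treatment assignment is cystectomy-free by selection and is counted at risk, so the rates are biased low. The size turns on an undefined term. Under the baseline reading, typical Phase 2 gaps cost about 3% to 7% of the rate, rising to about 11% at 12 months if everyone is at the 6-week limit. Under the first-ever reading, about 45% to 75% of the 12-month rate survives at assumed earlier-BCG shares of 50% to 20%. These figures rest on a constant hazard and on rates, shares and long gaps that the documents do not give; the direction does not depend on them.

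For repeat TURBT the fault is an unstated counting rule. The result is either contaminated by pre-trial procedures or based on a shortened post-randomization window. It is not time wrongly counted as event-free.

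The primary endpoint and the randomization-based cystectomy and TURBT analyses are unaffected. The change should be made, but no main conclusion depends on it.

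**What to change.** In SAP 7.2:

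1. Replace the original TURBT by the baseline staging procedure for the current occurrence. Every patient has one, and its date is verified at Phase 2 screening (Protocol 6.2.2).
2. For cystectomy, let each patient enter the risk set at randomization or treatment assignment (delayed entry, for example the ENTRY= option in SAS PHREG).
3. For the TURBT burden, count only TURBT or fulguration procedures after randomization or treatment assignment, and note that the window then holds less than 12, 18 or 24 months of follow-up.

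Alternatively, delete both sensitivity analyses; the main analyses do not need them.

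The cost is a few lines of SAP text and one programming option, with no new data. Intervals are slightly wider early in the curve, where few patients have entered. Nobody is at risk before the shortest gap, so the curve is conditional on an intact bladder up to that point; the report should say so.
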